#### RISK OF IMP

Ketamine has a very wide margin of safety: several instances of unintentional anaesthetic administration of overdoses up to 10 times that required have been followed by prolonged but complete recovery (see SPC).

Use with caution is indicated in patients with acute intermittent porphyria, increased cerebrospinal fluid pressure (as assessed by questionnaire), hyperthyroidism, pulmonary and upper respiratory infection as well a pregnancy therefore to further mitigate risk these are all exclusion criteria for the study (see section 5.2). Several drugs may interact with ketamine (e.g. barbituates, narcotics, CNS depressants) therefore currently daily use of these medications will be an exclusion criteria (see section 5.2).

Psychotomimetic symptoms or 'emergence reactions' are a key feature of ketamine administration. The psychological effects of anaesthetic doses vary between pleasant dream like states, vivid imagery to out of body

experiences and hallucinations. A review examining these phenomena across 450 volunteers given similar doses to those to be given in this study found only 6 incidences of such mental states that were unpleasant enough to require the infusion to be stopped, all of which remitted completely in the hours following the cessation of the infusion [20]. Patients with schizophrenia given doses of ketamine similar to those administered in this study have been known to have longer lasting psychotomimetic states [38] and for that reason psychosis in the patient and schizophrenia in the patient or a first degree relative are an exclusion criteria for the study (section 5.2). Emergence phenomena can be reduced in anaesthesia with the co-administration of a benzodiazepine; midazolam can be administered by the anaesthetist if the emergence phenomena are intolerable to the patient.

WOCBP will be included in this clinical trial as per the ICH M3 (R2) which suggests WOCBP can be included in clinical trials without developmental toxicity in studies where there is intensive control for pregnancy. Any risks will be mitigated by the use of contraceptives and pregnancy testing. Ketamine is indicated for use in caesarean section. A recent Cochrane Review [37] compared ketamine for forceps delivery to other analgesics and found no difference in maternal or neonatal outcomes. However, preclinical data from rats given extremely high doses indicate some neurotoxicity in rats. The current trial will use methods of birth control which result in low failure rates of less than 1% per year (See Inclusion criteria section 5.1), if pregnancy is detected then participants will be immediately excluded.

The summary of product characteristics advises caution in patients with neurotic traits or psychiatric illness (e.g. schizophrenia and acute psychosis). To mitigate risks against this risk and risk of potential suicide the protocol will exclude patients with these conditions as well as those who have suicidal ideation. At screening, the Columbia Suicide Severity Rating Scale will be used to assess suicide ideation. As patients at risk of suicide will be excluded, this tool will not need to be done at every assessment point as we have mitigated this risk from the outset. Additionally we will be monitoring depressive symptoms throughout the trial (Beck Depression Inventory and Hamilton Depression Rating Scale). The population group being studied are alcohol dependent individuals where alcohol use will be the primary disorder and not depression. The IMP (Ketamine) is an anti-depressant drug and has indeed been shown to have efficacy at reducing suicidal ideation in individuals with treatment resistant depression thus we feel the risk of increased suicidal ideation from ketamine is minimal.

*All other risks related to trial design and methods*  
*i) Risks from study procedures*

The table below summarises the risks and mitigations of all tests above standard care that are being performed:

Intervention	Potential risk	Risk Management
Cannulation and Venepuncture	Cannulation is required for administration of IMP and placebo. Plasma samples will be taken 13 times during the course of this study. Both are accompanied with a risk of discomfort, bruising, excessive bleeding, fainting or feeling lightheaded, hematoma & infection	Cannulation will be performed by an experienced anaesthetist and staff trained in venepuncture. Venepuncture risks will be managed using standard clinical care precautions which include wearing protective clothing, hand and surface hygiene. Risks to participants from venepuncture will be managed using standard clinical care. Non clinical staff performing venepuncture will receive appropriate training. Furthermore, in an effort to mitigate these risks, the participant information sheet (PIS) will make reference to these risks and inform people who have previously suffered complications during venepuncture or who have a fear of needles that they should not take part. Every effort will be made to make participants feel comfortable before, during and after cannulation and venepuncture by encouraging participants to relax and talking through any concerns they have about the procedure.  Trust incident reporting will apply and be followed in the event of patient/staff needle stick injury.
SCRAM-X bracelet	Participants will have their alcohol use over active treatment monitored via the SCRAM-X bracelet worn on the ankle. The wearer may not soak in the bath or swim.	Inclusion criteria require patients to be willing to wear the bracelet for active treatment.  The researchers who fit the bracelet will be extensively trained in fitting the bracelet

	Wearing the bracelet carries with it a risk of discomfort. It can cause bruising, pain and scars from it rubbing against the skin.	by colleagues at the health monitoring company Alere. Patients will be fully informed of the potential discomfort and the implications of wearing the bracelet in the participant information sheet. . Participants will be trained in how to clean under the bracelet to ensure that the risk of any skin problems is mitigated.
Psychological therapy	Psychological therapy may cause transient distress as the participant discusses sensitive and upsetting material	Participants will be informed that they do not have to discuss material they are not comfortable discussing. Trained psychologists with experience of psychological therapies will administer the therapy and be supervised by a consultant clinical psychologist with over 20 years experience in the field of treatment of alcohol use disorders.

*ii) Data risks*

Potential data risks include breach of participant confidentiality through inappropriate collection or storing of data. In order to minimise these risks, all researchers are GCP trained. Confidentiality will be ensured using standard procedures (e.g. password protected computers and data storage, all electronic data coded numerically so that individual participants cannot be identified; consent forms will be kept in secure locked cupboards in locked rooms). Any publications will similarly use anonymised data. The trial is occurring at two sites which facilitates data security. We appreciate that data about illicit drug use is sensitive and our security measures are appropriate to this.

The investigator will ensure quality of the study data with respect to inclusion/exclusion criteria, protocol adherence, data collection and storage, and all physical data collected as part of this trial will be entered into a Red Pill database designed by sealedenvelope.com with quality control checks.

The trial will be monitored by an appointed external monitor according to a monitoring plan developed by the sponsor and risk assessment of the trial. These risks will be further minimized by the use of a short trial duration

and finite follow up. Agreements are in place with the laboratories (ABS Laboratories, SCRAM-X and Alere) who will handle data from the study externally to ensure they agree to comply with confidentiality and relevant data protection acts.

Anonymised data collected from the SCRAM-X will be transferred to the UK study centre (Alere) and transferred to the US via a secure firewalled server for collation and then returned to Alere where it will be transferred securely to the study team. The patient information sheet will explain this to the patient and specific consent for anonymised data to go to the US will be sought.

Data collection using the SCRAM-X and of biological samples will be done in accordance with relevant UK confidentiality and data protection acts. Data collected with the bracelet will be entered anonymously into the Microsoft Access database. The patient information sheet will explain the measures taken to protect the patients' identity and collected data.

Biological samples will be labelled using anonymous patient IDs and will be sent by secure courier within the UK to the head analyst at our central laboratory (ABS Laboratories) who have reliably analysed biological samples for many of our previous research projects and is both regulated and accredited.

*Consent:* Standard procedures will be used whereby participants have a minimum of 24 hours after reading the patient information sheet before deciding whether to take part and giving consent. They will be encouraged to discuss their participation with significant others. All researchers appointed with this project have previous experience taking consent from patients.

#### *Treatment*

The participant information sheet will state that the trial design does not allow for switching of participants in the placebo arm to the active arm at the end of the trial. This is because neuropsychological measures are subject to repeated practice effects. However if the active treatment is successful, participants would be informed if a large scale clinical trial is subsequently initiated.

#### *Patient Group*

Although we have excluded patients with suicidal ideation or any other current psychiatric diagnosis apart from depression or anxiety, as this is an alcohol dependent population it is possible that they may experience worsening of their mental state during the study duration. If we observe or if patients report any changes in mental state at any of the study visits which we would deem as putting themselves or others at risk then we will refer them back to their medical care provider (e.g. Consultant Addiction Psychiatrist if referred from substance misuse services or GP if self-referral).

### 3 Objectives

Primary objectives:

- 1) To obtain preliminary data on whether ketamine is effective in promoting and prolonging abstinence in alcohol dependent patients following detoxification.
- 2) To assess safety and tolerability of ketamine in alcohol dependence

Secondary objectives:

- 1) To make an early assessment on likely compliance to a combined ketamine and relapse prevention based cognitive behavioural therapy (CBT)
- 2) To obtain preliminary data as to whether ketamine alone is as effective as a combined ketamine and psychotherapy treatment.

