#### *Enhancing the uptake of psychological therapy*

Psychosocial therapies are currently the mainstays of treatment for alcohol dependence but are of limited effectiveness, which may partly be because they depend on the brain's capacity for neuroplastic change [63]. Psychological therapies in alcoholism are also less effective in individuals with cognitive impairment [64]. Undergoing learning based psychological therapy during the period of neurogenesis and synaptogenesis, which commences around two hours after an acute dose of ketamine [53], may facilitate its uptake as the brain is primed to make new connections and learn new information. Increased synaptogenesis has been linked with improved memory [e.g. 65; 69]. Therefore ketamine may enhance the uptake of psychological therapy in the hours following an acute dose by making the brain more receptive to new learning.

The notion that treatments that stimulate neurogenesis and synaptogenesis in this manner may work synergistically with psychological therapies is becoming more accepted [90] and may represent a future paradigm shift in the treatment of mental health problems. Historically, approaches to treating alcoholism that involve psychological therapy and provoke neurogenesis have enjoyed some success [see e.g. 91 for a review] but it is only recently that the biological mechanisms have been elucidated. In order to examine whether enhancing the uptake of therapy is the mechanism by which ketamine is effective in alcoholism we have included a ketamine + 'no therapy' arm in the trial. These data will have considerable implications not only for alcohol dependence, but also

depression as this may suggest a similar psychotherapy plus ketamine approach may enhance the effectiveness of ketamine treatment.

*Additional advantages of ketamine: glutamatergic actions*

Ketamine also acts as an antagonist of the glutamatergic N-methyl-d-aspartate receptor. Glutamatergic activation and glutamate receptor up-regulation contribute to alcohol dependence and withdrawal [66]. Acute detoxification is associated with a hyperglutamatergic effect that NMDA-receptor antagonists have been shown to normalise [66]. Excess glutamate is known to have toxic effects, and ketamine may protect against some of these adverse effects.

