S+ Ketamine hydrochloride packaged as: Ketalar ® for Injection. The total amount to be delivered will be calculated on the basis of the patient's weight (0.8 mg/kg). Site pharmacy will order ketamine and dispense per patient, added to saline (0.9%) to make up to 50ml in syringes for the infusion pump. For patients allocated the placebo, site pharmacy will prepare a 50ml saline (0.9%) solution in syringes for the infusion pump. Doses will be administered using a computer controlled infusion pump. Participants will be given the option of whether they'd like to listen to non-vocal instrumental music during the infusion to block out environmental noise.

**Relapse Prevention Based Psychological Therapy:** A seven session manualised intervention and accompanying workbook developed with alcohol specialist clinical psychologists (the supporting documents will give the details for manual and workbook). The aim of these 7 sessions is to help to develop an enjoyable and meaningful life without alcohol. It focuses around two broad themes. The first theme relates to relapse prevention, i.e. skills and strategies to reduce the likelihood of relapse and maintain abstinence. The second theme focuses on promoting well-being and deals with issues such as purpose, meaning and life enjoyment, along with skills for coping with life's day-to-day problems and stresses.

*Session 1:* This session focusses on introducing the concepts of high risk situations and triggers as well as on planning your activities.

*Session 2:* This session focusses on recognising high risk situations and planning effective coping responses. In addition we identify essential resources for sobriety.

*Session 3:* The aim of this session is to develop further understanding of the role of thinking in drinking and how thinking biases can lead to unhelpful feelings and behaviour. In this session we also work on developing effective problem solving skills.

*Session 4:* The aim of this session is to develop general skills to recognise urges and craving and to plan an effective response. In this session we also introduce relaxation techniques and the concept of mindfulness.

*Session 5:* The aim of this session is to identify early warning signs of possible relapse. We also introduce the Demand Control Support model of stress to enhance insight into stress and ways of managing stress.

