*Session 6:* This session focusses on lapse management and developing emergency plans aimed at preventing full relapse and we work on enhancing life enjoyment and satisfaction.

*Session 7:* In the final session we look at roles and identities and introduce another mindfulness practice. We then develop a plan for the next three months

***Education control*** will be a 7 session educational programme educating patients about the risks of alcohol use and the effects of alcohol on the body (the supporting documents will also provide more detail).

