### **11.2 Data collection tools and source document identification**

Data to be collected can be found in sections 7.5 and 7.7. Every effort will be made to maximise completeness of data. Trial data will be collected in an Electronic Case Report Form hosted on sealedenvelope.com, prepared using their “Red Pill” service ([www.sealedenvelope.com/redpill](http://www.sealedenvelope.com/redpill)). Source data documents will be defined at site prior to the start of the trial.

Full details of source data and documentation will be identified in a separate source document identification list but in summary will comprise of the following:

- Patient Clinical Record (medical notes)
- Trial specific source data worksheets and trial specific logs

- Laboratory test print outs
- Questionnaires and measurement scales
- Encrypted memory stick containing computer tasks data files and SCRAM-X data

Data to be recorded in the source data first and then transcribed into the CRF:

- Patient demographics; age, date of birth and initials
- Medical history including drug use, alcohol use, smoking
- Physical examination
- Patient eligibility assessment
- Allergies
- Concomitant medication
- Study IMP treatment
- Therapies: Psychoeducation Therapy, Relapse-prevention based CBT
- Clinical Assessment measurements: Vital signs, Blood and urine screen. On infusion visits (visits 2, 4 and 6) continuous monitoring of vital signs will occur through the infusion until the participant has recovered. This monitoring will be recorded on a standard observation chart and will be stored as source data. The eCRF will record 3 sets of readings, one prior to the infusion, another after the infusion terminates, and then finally after the participants recovery.
- Adverse Events (refer to section 10)
- Assessment tools:
  - Pattern Recognition Test
  - Stop Signal Reaction Time
  - Delay Discounting (monetary choice questionnaire)
  - Working Memory (digit span WAIS-IV)
  - Prose Recall
  - SCRAM-X checks
  - BPRS
  - PSI
  - Adverse events VAS
  - Craving VAS
  - Fagerstrom smoking
  - Timeline follow Back
  - Drink diary
  - Reasons for drinking questionnaire
  - Columbia Suicide Severity Rating Scale
  - BDI
  - HAM-D
  - POMS

- STAI
- SF-12
- ACQ-NOW

The following data to be collected in the source documents but will not be collected in the CRF:

- Adverse events that are expected for the IMP and which are not serious and listed in section 10

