### **13.3.2 Primary outcome analysis**

There are two primary outcomes: (i) proportion relapsed (recommenced using alcohol) at 6-month follow-up; and (ii) percentage of days abstinent at 6-month follow-up (the denominator being 175 days). The proportion of relapsed participants at 6-month follow-up will be reported as a percentage for each arm, as well as for the ketamine arms combined and

the psychotherapy arms combined. Although no formal power calculations for a between-group analysis have been performed, the proportion of relapsed participants at 6-month follow-up will be expressed as a relative risk (RR) with a 95% confidence interval for the following comparisons: (i) all ketamine participants versus all non-ketamine participants; (ii) ketamine + psychotherapy participants versus ketamine + non-psychotherapy participants; and (iii) ketamine + psychotherapy participants vs. placebo + no psychotherapy participants. These analyses are purely exploratory and should be viewed with caution both in the light of lack of power and multiple testing. Percentage of days abstinent at 6-month follow-up will be reported descriptively in the same way by arm and combination of arms; additionally, the between-group mean differences and 95% confidence intervals will be reported for the comparisons set out above; again, these analyses should be regarded as exploratory. The primary analysis will be an intention-to-treat (ITT) complete case analysis including all randomised participants. A secondary analysis will be conducted including only those participants deemed to have completed to a sufficient degree their allocated interventions, that is, a per protocol analysis. All analyses will be performed by a statistician who is blinded to the treatment allocations and will be performed using Stata v.13.

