4.1 Interventions

KARE has two forms of intervention, a drug intervention and a psychotherapy intervention. The active drug intervention is ketamine, an anaesthetic/analgesic drug, to be administered intravenously. The placebo control

is saline. As well as a drug intervention the participants will receive concurrently either a psychotherapy intervention, or a psychoeducation control intervention. Hence, there are four combinations: (i) ketamine + psychotherapy; (ii) ketamine + psychoeducation; (iii) placebo + psychotherapy; (iv) placebo + psychoeducation. Participants will receive their allocated drug infusion in 3 doses over 3 weeks. Participants will concurrently receive either psychotherapy or psychoeducation control. The trial will be performed at two sites: Devon (Royal Devon & Exeter Foundation NHS Trust) and London (UCLH).

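### Secondary objective 2 asks about 'ketamine alone', but no arm receives ketamine without a session programme

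*Protocol*

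**What the plan says.** Secondary objective 2 has the same wording in the protocol Summary, protocol section 3 and SAP 5.1: "To obtain preliminary data as to whether ketamine alone is as effective as a combined ketamine and psychotherapy treatment".

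Protocol 2.4, under the uptake of psychological therapy, argues that learning-based therapy in the hours after a dose "may facilitate its uptake as the brain is primed to make new connections and learn new information". To examine that mechanism, it says, "we have included a ketamine + 'no therapy' arm in the trial".

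The arms are listed in SAP 4.1 as "i) ketamine + psychotherapy; (ii) ketamine + psychoeducation; (iii) placebo + psychotherapy; (iv) placebo + psychoeducation". Protocol 7.6 describes the psychotherapy as "A seven session manualised intervention and accompanying workbook", and says that the education control "will be a 7 session educational programme educating patients about the risks of alcohol use and the effects of alcohol on the body". Under SAP 4.4 the trial psychologists at each site deliver both. Protocol 11.2 enters the two side by side in its data list: "Therapies: Psychoeducation Therapy, Relapse-prevention based CBT".

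Protocol 13.3.2 plans three comparisons. The second sets ketamine plus psychotherapy against a ketamine group labelled non-psychotherapy. The third is "ketamine + psychotherapy participants vs. placebo + no psychotherapy participants". SAP 4.5 (vi) (b) and (c), and SAP 6.2, plan the same two comparisons and call the control psychoeducation.

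**The concern.** The objective and the mechanism argument both depend on a group given ketamine and nothing else. The group that stands in for it is allocated seven sessions on alcohol and its effects. The question asked and the contrast planned are therefore different.

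The difference matters because of the protocol's own theory. If ketamine makes the brain readier to learn, that readiness could serve an education session as well as a therapy session. Both ketamine arms would then carry the mechanism that the 'no therapy' arm was meant to switch off. Similar results in the two arms could mean that psychological sessions add nothing to ketamine. They could equally mean that both kinds of session help to a similar degree. The objective as worded points the reader to the first explanation, and the data could not tell the two apart. Protocol 13.2.1 presents the trial as an early indicator of whether a larger trial is warranted, so the misreading could carry forward.

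**Working it through.** **Step 1. What each ketamine arm is allocated.**

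| | Ketamine + psychotherapy | Ketamine + psychoeducation |
|---|---|---|
| Drug | ketamine infusions | ketamine infusions |
| Sessions (protocol 7.6) | 7 | 7 |
| Delivered by (SAP 4.4) | trial psychologists | trial psychologists |
| Content | relapse prevention and well-being | risks and bodily effects of alcohol |

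The two placebo arms have the same two programmes. Arms with ketamine and no sessions: 0 of 4. Participants so allocated: 0 of 96. The difference in number of sessions is 7 − 7 = 0. Neither document gives session lengths, so only the number of sessions is shown to match. SAP 4.4 mentions two sessions a week for three weeks, which is 2 × 3 = 6 rather than 7. That count also applies to both programmes and is not zero.

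**Step 2. What the contrast estimates.** Take an additive scale, such as the difference in percentage of days abstinent, with higher values better. On a ketamine background let

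- D = expected outcome with ketamine and no sessions,
- A = non-specific effect of attending sessions,
- P = specific effect of the psychotherapy content,
- E = specific effect of the education content, including any enhancement by ketamine.

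Then:

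- ketamine + psychotherapy = D + A + P
- ketamine + psychoeducation = D + A + E
- planned contrast (b) = (D + A + P) − (D + A + E) = **P − E**
- quantity named in objective 2 = (D + A + P) − D = **A + P**
- shortfall = (A + P) − (P − E) = **A + E**

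The term A is shared by both arms and drops out. The term E is subtracted. If attendance or education helps, contrast (b) understates what the combined treatment adds to ketamine alone, by A + E. In the limiting case E = P the contrast is zero however large A + P is. No arm identifies D, so A + E cannot be estimated from this trial.

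**Step 3. Contrast (c).** Its reference group is placebo plus education, so an education effect on a placebo background is subtracted there. It does not isolate ketamine without sessions either.

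**Step 4. Labels side by side.** The same control condition is called:

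- ketamine alone: protocol Summary, protocol section 3, SAP 5.1
- 'no therapy': protocol 2.4
- non-psychotherapy and no psychotherapy: protocol 13.3.2
- no psychotherapy, with alcohol education in brackets: SAP introductory text
- psychoeducation: SAP 4.1, 4.5, 6.2 and the PE columns of Tables 4 to 8

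**Step 5. Does the precision caveat cover this?** The protocol's own figure reproduces. With 24 per drug arm and relapse of 50% against 25%, 0.25 ± 1.645 × √(0.5 × 0.5/24 + 0.25 × 0.75/24) gives 2.8% to 47.2%, matching the stated 3% to 47%. For contrast (b), the assumed 50% drop-out leaves 12 per cell. If the true relapse rates were equal, the 95% half-width without site adjustment would be:

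- at 25% relapse: 1.96 × √(2 × 0.25 × 0.75/12) = 34.7 points; CI around a relative risk of 1, 0.25 to 4.0
- at 50% relapse: 1.96 × √(2 × 0.5 × 0.5/12) = 40.0 points; CI around a relative risk of 1, 0.45 to 2.2

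With no drop-out (24 per cell) the half-widths are 24.5 and 28.3 points. A larger sample narrows these intervals, but they remain intervals for P − E. Precision and target are separate matters.

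**The case against.** The comparator is not hidden. The protocol Summary calls it a psychoeducation control, protocol 7.6 describes it, the SAP's introductory text glosses it as alcohol education, and SAP 4.1 lists it. The authors put 'no therapy' in quotation marks, which suggests shorthand, and the phrase 'ketamine alone' appears in the objective and not as an arm name. A session-matched education control is a legitimate choice. The objective asks only for preliminary data. The comparisons are labelled exploratory, no p-values will be reported, and no equivalence claim is planned.

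All of this is true, and it limits the weight of the point. It does not remove it. The exploratory caveats in protocol 13.3.2 and SAP 4.5 concern power and multiple testing, and say nothing about what the contrast compares. SAP 5.1 repeats the objective unchanged, although the SAP labels the arms correctly elsewhere.

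A reader might infer more than the documents support:

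- *That the SAP mislabels its contrasts.* It does not. SAP 4.5, 6.2 and the tables name psychoeducation; the loose contrast labels are in protocol 13.3.2.
- *That any education effect cancels out of contrast (b).* Only non-specific effects common to both programmes cancel. An education effect, or its interaction with ketamine, arises in one arm and is subtracted.
- *That contact time is matched.* Only the number of sessions is.
- *That a small contrast (b) would lead to psychological sessions being dropped.* No rule in either document says so. The risk is one of interpretation.

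**Conclusion.** Wrong as written, and minor. Objective 2 and the mechanism argument in protocol 2.4 refer to a condition that none of the four arms, and none of the 96 planned participants, is allocated. The planned contrast is valid for psychotherapy against alcohol education on a ketamine background. It estimates P − E where the objective names A + P.

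The direction of the resulting error rests on one assumption that the documents allow but do not establish: that education or attendance has some benefit. Under it, the contrast leans towards the conclusion that ketamine alone is as effective. If both A and E were zero, the contrast and the objective would coincide. The size of A + E cannot be worked out from the documents. No fault in the arms, the allocation or the planned estimates follows from this point.

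**What to change.** 1. In the protocol Summary, protocol section 3 and SAP 5.1, restate secondary objective 2 as a comparison of ketamine plus alcohol education with ketamine plus relapse-prevention CBT.
2. In protocol 2.4 and 13.3.2, replace the no-therapy, non-psychotherapy and no-psychotherapy labels with alcohol education. The SAP contrasts and tables need no change.
3. Add to SAP 4.5 that contrasts (b) and (c) do not estimate the effect of ketamine without psychological sessions, and that a small contrast (b) will not be reported as showing that ketamine alone suffices.

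Arms, visits, sample size and analyses stay as they are. The costs are a narrower claim and a wording amendment. Under protocol section 16 the sponsor would assess whether the protocol change is substantial, and a substantial one needs ethics and regulatory approval. The SAP change would be recorded and approved by the trial management group under protocol 13.6.
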